Randomised patients will be followed up to death or 180 days post-randomisation. Data collection will be restricted primarily to those variables necessary to define clinical patient characteristics including: baseline demographics, primary diagnoses, physiological parameters, diagnostic interventions, therapeutic interventions and documentation of deaths and other adverse events.

Patients and/or their legal surrogate will be asked to provide three possible points of contact (home and close family contact details) to the research staff prior to discharge. For patients discharged alive from ICU, follow-up will be restricted to information concerning duration of hospital stay and vital status at hospital discharge, 90 days and 180 days post randomisation. In addition, patients (or a proxy – generally a close family member) that are alive at 180 days after randomization will be interviewed by the site RC using a simple standardized structured telephone questionnaire to measure quality of life EQ5D [48].

Data variables collected

- Demographic data:
 - Identity (initials, study number, date of birth, gender, postcode)
 - Blood group: A, B, O, AB, Rhesus status (positive or negative)
 - Alloantibodies (if present)
 - Co-morbidities: heart disease including angina, myocardial infarction and previous CABG, immuno-compromised
 - Ethnicity (for patients enrolled in New Zealand only)
- Hospital data
 - Hospital admission and discharge dates
 - Hospital discharge destination
- ICU data
 - ICU admission and discharge dates
 - Acute Physiology and Chronic Health Evaluation III [APACHE III] score and risk of death at ICU admission
 - Acute Physiology and Chronic Health Evaluation III [APACHE III] diagnosis code at admission
 - Current “unstable or active” heart disease –(cardiac arrest, arrhythmia, cardiogenic shock, angina, acute myocardial infarction)

- Sequential Organ Failure Assessment [SOFA] score at randomisation and daily during ICU admission
- Haemoglobin at ICU admission
- Requirement of invasive mechanical ventilation at randomisation
- Duration of mechanical ventilation
- Requirement of renal replacement therapy at randomisation
- Duration of renal replacement therapy
- Requirement of catecholamines at randomisation
- Duration of catecholamine administration
- Blood stream infection (date and pathogen)
- Transfusion information
 - Haemoglobin pre transfusion episode
 - Date and time of each RBC unit transfused

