We estimated the baseline mortality using the prospective ANZ observational study data [3]. Over 5 weeks in 2008, 757 patients were recruited. The exclusion criteria of TRANSFUSE leaves 45% recruitable patients. These patients had a hospital mortality of 25% and we conservatively estimate 90-day mortality to be 28%. Our sample size calculation is based on a 15% relative decrease in 90-day mortality, or an absolute decrease of 4.2% from 28% to 23.8%. This effect size would be clinically highly relevant (Number needed to treat to save one life [NNT]=24). This relative decrease is much less than observed in the Koch study (30% RRR) [28], and in our observational study where we found a mortality of 21.3% in the older three quartile versus 13.2% in the freshest quartile (38% RRR) [3]. With a type I error of 0.05 and a type II error of 0.1 (power 90%), the required patient number is 2332 per group. According to our previous studies [54, 55], loss to follow up should not exceed 5%, giving an accurate number of 4898 patients which has been rounded up to 5000 patients.

Statistical and analytical plan

This study will be analysed on an intention-to-treat basis. Analysis will primarily be conducted using SAS version 9.2. (SAS Institute Inc., Cary, NC USA). Baseline comparisons will be performed using chi-square tests for equal proportion, student t-tests for continuously normally distributed variables and Wilcoxon rank sum tests otherwise. The primary outcome, 90 day all-cause mortality will be analysed using a Chi-square test statistic, with results reported as frequencies and percentages per arm. Adjustment for strata (centre) will be made using logistic regression for binomial outcomes and Cox Proportional Hazards regression for time to event data with results reported as Odds Ratios (95% CI) or Hazard ratios (95% CI) respectively. In the unlikely event that baseline imbalances are found to exist between treatment groups, sensitivity analysis will be performed with imbalanced variables included as covariates. A two-sided p-value of 0.05 will be considered to be statistically significant. Additionally a per protocol analysis will be undertaken to account for patients with alloantibodies for whom freshest blood is unavailable. A detailed statistical analysis plan will be published prior to analysis being performed.

Subgroup analyses

A priori subgroup analyses will include:

- Group O versus non group O
- Illness severity according to APACHE III and SOFA scores

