APPENDIX 1 – SCHEDULE OF EVENTS

Assessments / Procedures		ICU admission	Pre-1 st RBC transfusion	Daily ICU Admission	ICU Discharge	Hospital Discharge	Follow-up – 28 days post-randomisation	Follow-up – 90 days post-randomisation	Follow-up- 180 days post randomisation
Screening log		X							
Inclusion & Exclusion criteria			X						
Demographic data			X						
Primary diagnosis		X							
Comorbidities			X						
Physiological parameters		X	X						
APACHE III		X							
SOFA			X	X					
Patient's blood group (ABO, Rh)			X						
Randomisation			X						
RBC Transfusion (each unit)	Haemoglobin pre-transfusion		X	X					
	Time & date of transfusion			X		X			
	RBC blood group (ABO, Rh)			X		X			
	Pack number			X		X			
	Collection and expiry dates			X		X			
	Blinding status (units checked by non-bedside nurse)			X					

Assessments / Procedures	ICU admission	Pre-1 st RBC transfusion	Daily ICU Admission	ICU Discharge	Hospital Discharge	Follow-up – 28 days post-randomisation	Follow-up – 90 days post-randomisation	Follow-up- 180 days post randomisation
Adverse Events			X					
Serious Adverse Events			X					
Number of units (ml) FFP post-randomisation			X					
Number of units platelets post-randomisation			X					
Febrile non-haemolytic transfusion reaction			X					
Requirement for catecholamine		X	X					
Requirement for Invasive Ventilation		X	X					
Requirement for Renal Replacement Therapy (RRT)		X	X	X				
Blood stream infection (date(s), pathogen(s))			X					
Vital status & cause of death				X	X	X	X	X
EQ5D								X

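### SOFA at randomisation is collected but enters no pre-specified overall estimate of 90-day mortality: a cheap gain in power missed, not an error

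*Combined protocol and SAP*

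**What the plan says.** Under Statistical and analytical plan, "The primary outcome, 90 day all-cause mortality will be analysed using a Chi-square test statistic", reported as counts and percentages by arm. The next step is "Adjustment for strata (centre) will be made using logistic regression for binomial outcomes", giving odds ratios with 95% CIs. The natural reading is that the chi-square is the primary test and the centre-adjusted odds ratio accompanies it.

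Other covariates can enter in one way only: "In the unlikely event that baseline imbalances are found to exist between treatment groups, sensitivity analysis will be performed with imbalanced variables included as covariates". No threshold for imbalance and no list of variables is given. Under Subgroup analyses, severity appears as "Illness severity according to APACHE III and SOFA scores".

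The data exist. Data variables collected lists "Sequential Organ Failure Assessment [SOFA] score at randomisation and daily during ICU admission" and "Acute Physiology and Chronic Health Evaluation III [APACHE III] score and risk of death at ICU admission". In Appendix 1 the SOFA and Randomisation rows are both marked under "Pre-1 st RBC transfusion", while APACHE III is marked at ICU admission.

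The section also states: "A detailed statistical analysis plan will be published prior to analysis being performed". That plan is not in the text supplied, so this point concerns only the method stated here.

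**The concern.** In a critically ill population a severity score taken at randomisation would be expected to predict death. Putting a prognostic baseline covariate into the main model, fixed in advance, raises power and narrows the interval for a marginal effect without recruiting anyone. Here the covariate is already on the case report form, but the stated plan uses it only to define subgroups or, possibly, in a sensitivity analysis.

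The imbalance clause does not fill the gap. It yields only a sensitivity analysis, its trigger is undefined, and it selects covariates by how unequal they look between arms. The gain comes from how strongly a covariate predicts the outcome, whether or not the arms happen to differ on it.

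At stake is some power at the design effect, more if the true effect is smaller, and a tighter risk difference if the result is null. The rationale treats a null result as informative for practice.

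**Working it through.** **Inputs.** From Sample size calculation: 28% vs 23.8%, type I error 0.05 (two-sided, per the analysis plan), power 90%, 2,332 per group, loss at most 5%, 5,000 enrolled. Evaluable per arm: 5,000 × 0.95 / 2 = 2,375. The AUC of SOFA for 90-day death is not in the documents; it is assumed and shown as a range.

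**1. The plan's own figure.** Let d = 0.042, mean risk p̄ = 0.259, v₁ = 0.28 × 0.72 = 0.2016, v₂ = 0.238 × 0.762 = 0.1814.
- n₀ = [1.96√(2p̄(1−p̄)) + 1.2816√(v₁+v₂)]² / d² = 2,284.3, that is 2,285 per group.
- With continuity correction: (n₀/4)[1 + √(1 + 4/(n₀d))]² = 2,331.7, that is 2,332. The stated figure reproduces.

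**2. Chi-square as planned, n = 2,375 per arm.**
- SE of the risk difference = √(0.38296/2,375) = 0.01270; half-width = 1.96 × 0.01270 = 2.49 points.
- Power = Φ[(0.042 − 1.96√(2 × 0.19192/2,375)) / 0.01270] = Φ(1.345) = 91.1%.

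**3. Adding severity, risk-difference scale.** Treat severity as a normal score with standard deviation SD on the logit scale, set to give the assumed AUC at mean mortality 25.9%. R² = Var(individual risk) / [p̄(1−p̄)]. Both variances in step 2 are multiplied by (1 − R²). Equivalent extra patients = 4,750 × [1/(1−R²) − 1].

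| Assumed AUC | SD | R² | Power | Half-width (points) | Equivalent extra patients |
|---|---|---|---|---|---|
| none (chi-square) | – | – | 91.1% | 2.49 | – |
| 0.60 | 0.36 | 0.024 | 91.7% | 2.46 | 119 |
| 0.63 | 0.48 | 0.042 | 92.2% | 2.44 | 205 |
| 0.70 | 0.78 | 0.100 | 93.6% | 2.36 | 528 |
| 0.74 | 0.99 | 0.146 | 94.7% | 2.30 | 811 |
| 0.79 | 1.29 | 0.217 | 96.2% | 2.20 | 1,318 |

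**4. The same adjustment, odds-ratio scale.** Unadjusted: OR = (0.238/0.762)/(0.28/0.72) = 0.803; SE of log OR = √[1/(2,375 × 0.2016) + 1/(2,375 × 0.1814)] = 0.0664. Adjusted values come from the information matrix of a logistic model with treatment and severity, calibrated so that marginal risks stay at 28% and 23.8%.

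| Assumed AUC | Conditional OR | SE of log OR |
|---|---|---|
| unadjusted | 0.803 | 0.0664 |
| 0.60 | 0.799 | 0.0672 |
| 0.70 | 0.784 | 0.0700 |
| 0.79 | 0.756 | 0.0751 |

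The standard error goes up, but the log odds ratio grows faster. |ln 0.803|/0.0664 = 3.30, against |ln 0.784|/0.0700 = 3.48 at AUC 0.70, so power rises from Φ(3.30 − 1.96) = 91% to Φ(3.48 − 1.96) = 94%.

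**5. Simulation check.** 2,000 trials of 4,750 patients for each SD of 0.48, 0.78, 0.99 and 1.29. Chi-square power was 90.9%, 91.4%, 91.5% and 91.0%. Severity-adjusted logistic power was 92.4%, 93.5%, 94.6% and 96.3%. Half-widths of the standardised risk difference were 2.44, 2.36, 2.30 and 2.20, against 2.49 unadjusted. The score was complete and correctly specified.

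**6. Centre alone.** For an assumed between-centre logit SD of 0.2, 0.3 or 0.5, the planned centre adjustment adds about 0.1, 0.3 or 0.7 points of power. It does not stand in for severity.

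**The case against.** The strongest objection is about scale. A reader might infer that the confidence interval the plan will report is wider than it need be. The documents do not support that. The only interval named for a binary outcome is for the odds ratio, and step 4 shows that adding SOFA raises the standard error of its logarithm by 1% to 13%. The narrower interval belongs to a standardised risk difference, which the plan does not report. This stands and limits the point: on the plan's own scale the gain is in power, and the adjusted odds ratio answers a different (conditional) question.

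Second, the size rests on an AUC that the documents do not supply, and missing or mis-modelled SOFA would shrink the gain. This also stands. At AUC 0.60 the benefit is negligible.

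Third, the trial already reaches its target, and an unadjusted test matched to the sample-size basis, with adjustment for the sole stratification factor, is coherent. True, so a reading that the trial is underpowered or the test wrong is not supported. But 90% applies only at the assumed effect. If the relative reduction were 10% (an assumption: 28% vs 25.2%), chi-square power at 2,375 per arm would be 58.9%, and 63.4% with adjustment at AUC 0.70.

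Fourth, the documents adjust elsewhere: APACHE III in the investigators' observational study, and known covariates in the Appendix 4 substudy. A reader might infer an inconsistency. That is weak support, since the observational model was controlling confounding and Appendix 4 names no severity score.

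Finally, the promised SAP may already deal with this. It cannot be checked here, so it should not be inferred that the final plan omits severity.

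**Conclusion.** The point holds as a cheap improvement. The stated plan has no pre-specified overall estimate of 90-day mortality that includes SOFA, and neither the severity subgroups nor the imbalance-triggered sensitivity analysis provides one.

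The gain over the chi-square is about 0.6 points of power and 0.03 points of risk-difference half-width at AUC 0.60, about 2.5 and 0.13 at AUC 0.70, and about 5 and 0.29 at AUC 0.79. These figures assume 2,375 evaluable patients per arm, the design mortality rates, and a complete, correctly specified score. The precision part applies only to a standardised risk difference.

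**What to change.** In the SAP, before unblinding:

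- Pre-specify a logistic model for 90-day mortality with treatment, centre and SOFA at randomisation. Fix the functional form of SOFA and the rule for missing values, including for patients randomised in the Emergency Department. Use only the value at randomisation, not later daily scores.
- From that model report the standardised risk difference with 95% CI, and the odds ratio labelled as conditional.
- Keep reporting the chi-square, and state which of the two analyses is primary. If it is the adjusted one, say how the interim comparison of mortality proportions relates to it.
- Use this fixed covariate set in place of covariates chosen by observed imbalance.

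SOFA is the natural choice because it is scheduled with randomisation. APACHE III is taken at ICU admission, which can follow randomisation for patients enrolled in the Emergency Department.

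Cost: SAP wording and a little analysis work, with no new data. It needs rules for missing SOFA and for small centres (about 50 centres are planned), and a clear statement of the estimand.

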Only a large multicentre RCT can address whether the age of RBC transfusion affects mortality. Accordingly the TRANSFUSE study will have important health policy implications regardless of the outcome, in Australia and internationally.

OBJECTIVES

Aim

This study aims to determine whether, compared to standard care, transfusion of the freshest available allogeneic RBC decreases mortality of patients admitted to ICU.

Hypothesis

In critically ill patients who require a RBC transfusion, compared to standard practice, the administration of the freshest available compatible RBC reduces 90-day patient mortality.

STUDY OUTCOME MEASURES

Primary outcome

90 day mortality

Secondary outcomes

1. 28 day mortality
2. Persistent Organ Dysfunction combined with death at 28 [47]
3. Days alive and free of mechanical ventilation at day 28 post randomisation
4. Day alive and free of renal replacement therapy at day 28 post randomisation
5. Blood stream infection in ICU (post randomisation)
6. Length of stay in ICU and in hospital post randomisation
7. Proportion of patients who suffer at least one febrile non-haemolytic transfusion reaction in ICU
8. EQ-5D score at day 180 post randomisation [48]

OVERALL STUDY DESIGN

Study design

TRANSFUSE-RCT is a multi-centre, randomised, double blind, controlled trial, testing the effect of the freshest available RBC compared to standard practice, on mortality in critically ill patients who require RBC transfusion.

Study treatments

- Freshest available blood group: These patients will receive the freshest available group-specific compatible RBC unit in the transfusion service.
- Standard care group: These patients will receive standard practice, which is the oldest available group-specific compatible RBC unit in the transfusion service.

Study population

ICU patients or emergency department patients accepted for ICU admission in participating hospitals who meet all inclusion criteria and have no exclusion criteria. The study will enrol 5000 patients, in approximately 50 centres in Australia and New Zealand (ANZ).

Our observational study indicated that the recruitment of 40 patients per week is feasible and conservative [3]. At such a rate study recruitment would be completed in approximately 2.5 years. Allowing for study set up (12 months), 90 day outcome assessments, monitoring and analysis, a study time period of 4 years is anticipated.

Inclusion criteria

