This Renal substudy of the TRANSFUSE trial provides a unique opportunity to evaluate the effect of age of RBC on the incidence, severity and duration of AKI in critically ill patients and may also elucidate mechanisms involved in the body's response to RBC transfusion, thereby enhancing the parent study results. Leveraging the infrastructure and study design of the TRANSFUSE trial, this substudy provides a highly cost-efficient opportunity to test a clinically important hypothesis which cannot be answered outside such a large RCT and which would be unlikely to be funded as a separate study.

Methods

Renal function will be assessed in the TRANSFUSE trial using the KDIGO (Kidney Disease, Improving Global Outcomes) classification system[71] and an additional question at 90 day follow-up on the need for ongoing renal replacement therapy. There are no additional procedures required for this substudy.

Inclusion criteria: The same as for the TRANSFUSE trial. All patients recruited to the trial at Australian, New Zealand and other overseas sites that agree to participate in this substudy will be included.

Exclusion criteria: The same as for the TRANSFUSE trial with the following addition: patients with pre-existing end stage renal failure (receiving chronic dialysis) and those already undergoing renal replacement therapy at randomisation will be excluded.

Measurements

Renal function: AKI will be classified using the KDIGO classification system, the latest consensus classification system for AKI which has now been validated and used extensively[71, 72].

Ongoing renal replacement therapy: A question has been added to 90 day follow-up to ascertain whether the patient is receiving ongoing renal replacement therapy.

The only additional data to collect would be baseline creatinine defined as the most recent creatinine pre-randomisation, then the highest daily creatinine thereafter when available during the ICU stay for a maximum of 28 days (the duration of the trial follow-up in ICU). Collection of routine available creatinine values will be performed for this period, with no extra dedicated blood collection required for the substudy. The use of renal replacement therapy while in hospital will also be recorded as part of the TRANSFUSE parent trial.

Outcome measures

Primary outcome:

Cumulative proportion of patients with any degree of AKI

Secondary outcomes:

- a) The proportion of patients who develop stage 3 AKI (KDIGO criteria)

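### Ventilation-free and RRT-free days have no pre-specified adjustment for support status at randomisation, which is already collected; the cost is precision on two secondary outcomes, not bias

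*Combined protocol and SAP*

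**What the plan says.** **Outcomes.** Secondary outcomes 3 and 4 (Study outcome measures) are days alive and free of mechanical ventilation at day 28 and "Day alive and free of renal replacement therapy at day 28 post randomisation".

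**Baseline data.** The ICU items under Data variables collected include "Requirement of invasive mechanical ventilation at randomisation" and "Requirement of renal replacement therapy at randomisation". The schedule of events (Appendix 1) places both before the first red cell unit.

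**Design.** Randomisation is 1:1 in variable blocks, stratified by centre only. Support status is not a stratum.

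**Analysis.** The plan reads "Adjustment for strata (centre) will be made using logistic regression for binomial outcomes and Cox Proportional Hazards regression for time to event data". It names no test, effect measure or model for a day count. Covariates other than centre appear only in a sensitivity analysis that depends on finding a baseline imbalance. Support status is not among the a priori subgroups. The section ends by promising a detailed SAP before analysis; that document is not part of what was reviewed.

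**Eligibility.** The parent exclusion list mentions neither chronic dialysis nor RRT at randomisation. The renal substudy (Appendix 4) adds both: patients with end-stage renal failure on chronic dialysis and "those already undergoing renal replacement therapy at randomisation will be excluded".

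**The concern.** Support status at randomisation is the starting state of the process that these two outcomes measure. A patient already ventilated, or already on RRT, will on average have fewer free days than one who is not, whichever blood is given. That difference adds variance to the treatment comparison, and a model containing the status removes it.

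Nothing in the plan does this. The centre adjustment is tied to two model types that do not apply to a day count, and the sensitivity analysis is triggered by imbalance. The precision gained from a prognostic covariate does not depend on an observed imbalance, so that provision does not recover it. At stake are wider intervals than necessary on the trial's two organ-support outcomes, and an analysis left open to later choice.

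**Working it through.** **1. The plan's own figure.** The only sample size calculation for the main trial is for 90-day mortality: 28% against 23.8%, 90% power, and "A two-sided p-value of 0.05 will be considered to be statistically significant". The usual two-proportion formula gives 2,285 per group; the continuity correction, n/4 × [1 + √(1 + 4/(n × 0.042))]², raises this to 2,332, as stated. Then 2 × 2,332 × 1.05 = 4,897.2, or 4,898, rounded in the plan to 5,000. The point here does not touch that calculation. No SD, target effect or power is stated for either free-days outcome.

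**2. Effect of adjustment.** Let ρ be the correlation between support status at randomisation and free days. Adjustment multiplies the standard error of the treatment difference by √(1 − ρ²). A comparison with 80% power unadjusted (a hypothetical reference, since the plan gives none) then has power Φ(2.80/√(1 − ρ²) − 1.96), where 2.80 = 1.96 + 0.84.

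**3. Plausible ρ.** The documents give none, so it was simulated from assumed inputs:
- 40–70% ventilated and 5–20% on RRT at randomisation;
- median support 4–10 days, lognormal with log-SD 1;
- new starts in 20% (ventilation) or 7% (RRT) of the others;
- 28-day mortality about 20–25%.

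This gave ρ of 0.21–0.44 for ventilation and 0.15–0.49 for RRT.

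**4. Results.** The last column is 5,000/(1 − ρ²).

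| ρ | ρ² | SE ratio | Power | Equivalent N for 5,000 |
|---|---|---|---|---|
| 0.15 | 0.0225 | 0.989 | 80.8% | 5,115 |
| 0.21 | 0.0441 | 0.978 | 81.7% | 5,231 |
| 0.35 | 0.1225 | 0.937 | 84.8% | 5,698 |
| 0.44 | 0.1936 | 0.898 | 87.7% | 6,200 |
| 0.49 | 0.2401 | 0.872 | 89.47% | 6,580 |

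The gain is therefore about 1 to 9 points, and it reaches about 5 points only from ρ of roughly 0.35.

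**5. A second set of assumptions.** The inputs here were 40–70% ventilated with a mean of 5–8 further days, 5–15% on RRT, and higher mortality in those on support. The share of variance explained (R² = ρ²) was about 0.04–0.20 for ventilation and 0.03–0.17 for RRT with no chronic dialysis. Scoring deaths as zero free days puts the result in the lower part of these ranges (0.04–0.12 and 0.03–0.09); counting the days alive puts it in the upper part (0.08–0.20 and 0.08–0.17). The plan does not say how deaths are scored. If half of those on RRT were chronic dialysis patients, R² could reach about 0.39, but the documents give no such share and no conclusion here rests on it.

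**6. Chance imbalance.** With 2,500 per arm, the standard error of the between-arm difference in prevalence is √(2 × 0.5 × 0.5/2,500) = 1.4 points at 50% prevalence and √(2 × 0.1 × 0.9/2,500) = 0.85 points at 10%. Large imbalances are unlikely, so the case rests on precision.

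**The case against.** The best reply is that the plan is silent here and makes no wrong choice: it names no comparison for free days, and it defers detail to a later SAP, where a covariate list would normally sit. That stands. A reader might infer that the plan commits to an unadjusted comparison; the text does not say so. But the section does set out tests, centre adjustment and subgroups, and as written it leaves these two outcomes without a method, so the recommendation is useful wherever the detail ends up.

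A second reply is that the sensitivity analysis handles imbalance. It does, if one is found. It is secondary and decided after seeing the data, and it does not supply the precision gain.

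Third, the size is assumed. That also stands: at the low end the gain is about one point.

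Two stronger readings are tempting. One is that the substudy exclusion proves chronic dialysis patients are in the parent trial. It shows only that the parent criteria admit them; no number is given. The other is that RRT-free days are settled in advance for everyone on RRT. For patients on acute RRT they are not, because time to coming off support is part of what the outcome measures.

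Finally, crossing about 50 centres with a binary status gives about 100 strata. At an average of 5,000/50 = 100 patients per centre and an assumed 5–20% on RRT, a centre has 5–20 such patients across both arms, and smaller centres fewer. The objection to sparse strata is sound and shapes the fix.

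**Conclusion.** The point holds as a free improvement of low severity. A baseline value that predicts the outcome is collected before the first unit, and the plan makes no provision to use it in the main analysis of two of its eight secondary outcomes. The loss is precision only: randomisation balances support status in expectation, so there is no bias, and the primary outcome and sample size are unaffected.

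Under assumed correlations of about 0.15–0.49, 80% unadjusted power becomes about 81–89%, with standard errors about 1% to 13% smaller (1 − 0.989 to 1 − 0.872). These figures rest wholly on assumed prevalence, duration of support and mortality, and on a hypothetical 80% reference. They apply to a mean-scale analysis and do not describe a rank test.

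**What to change.** In the statistical and analytical plan, or in the promised SAP before unblinding, state that:
- each free-days outcome is compared with a linear model on the day count, with treatment, centre and status on that same support at randomisation as separate terms, and robust or bootstrap confidence intervals;
- if a van Elteren test is preferred, it is stratified by support status, and sparse centre-by-status strata are avoided;
- as a supporting analysis, RRT-free days are reported in patients not on RRT at randomisation.

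The last item should not be described as matching the renal substudy population. The substudy excludes chronic dialysis separately and includes only agreeing sites. The RRT flag may also miss a chronic dialysis patient between sessions, and the listed co-morbidities do not include end-stage renal failure.

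The cost is wording. Both status items are already collected, so no further patients, visits or data are needed for these analyses. Identifying chronic dialysis patients reliably could need a further baseline item, but the fix does not depend on it.
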